7.2. Study Endpoints

7.2.1. Primary Study Endpoints

The accuracy for the classification of regions within the test panel that either were a reaction (reaction grade 1+) or not (grade 0).

[figure not shown]
7.2.2. Secondary Study Endpoints

- The accuracy for the classification of the test site region using a 5-point scale: Grades 0 – 4.
- Sensitivity
- Specificity
- False positive rate
- False negative rate
- Percentage early termination of testing
- Percentage of participants that removed patches early
- Adverse events related to allergen exposure
- Patient feedback on the testing process

Primary Hypothesis:

The AI algorithm will provide non-inferior performance measured by binary classification accuracy relative to the human performance.

To test the primary hypothesis, The primary hypothesis to be tested is the “agreement” between the clinical (in person) evaluation and the human review and AI predictions of the app captured images. Generalized estimating equations (GEE) will be structured to estimate the clustered accuracy using an identity link and robust variance estimator to account for the clustering within the database. The model will have a single predictor that indicates which reader (AI vs. human) is associated with the accuracy determination (a 1/0 with 1 indicating the “reader” reached the same conclusion as the expert, in person review). For the purpose of the primary outcome measure, the prediction from either the human or AI algorithm will be dichotomized into no reaction (grade 0) vs. any reaction (grades 1 – 4). The estimate and 95% CI for the “reader” effect will summarize the differential performance between the human and AI interpretations. For the AI algorithm to be considered non-inferior, a limit of inferiority of 5 percentage points will be used. The fitted model will be used to estimate the overall performance and 95% CI for the two readers. As shown in the figure, we desire both the human and AI performance to provide greater than 95% accuracy.

To supplement this analysis, the area under the receiver operating characteristic curve (AUC ROC) will be computed using the visual analog scale by test site determined by the human observer and the AI model’s output. DeLong’s test will be used to compare the differences in performance between these two approaches.

Secondary Hypothesis 1:

For the secondary endpoint of agreement on the 5 point clinical scale, unweighted and weighted Kappa will be used to estimate the degree to which the human and AI interpretations agree. The unweighted analysis will focus on the direct match on grade assigned to each of the test sites.

There is a block of standard measures of diagnostic performance (e.g., sensitivity, specificity). These statistics will be computed as is customary for similar studies. The calculations will be performed two ways when possible. First, each test site will be assumed to be statistically independent in the rating. For the neural network, this is how the algorithm functions. For the human reading, there may be some correlation among the ratings based on the reactions, if any, that are observed. To address this, an exploratory analysis will be conducted using generalized estimating equations to examine the impact empirically the intercorrelations may have on the estimated precision of the estimates (i.e., confidence interval width).

Safety data will be summarized by tabulating adverse events for the study. These will be categorized according to allergen related or study protocol related.

The secondary test sites include allergens, in novel combinations, that were tested in the primary test site. A secondary analysis will be conducted to quantify the agreement of reactions to the same allergens alone (primary test patch) and in combination (secondary test patch). Kappa will be used to quantify this agreement.

Finally, participant feedback on the study including the wearability of the patch on the forearm will be summarized using standard qualitative methods. This will include the extraction of key themes as well as listing open ended feedback provided to the study team by the participants.

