7.1. Sample Size Determination

The primary sample size is determined based on Phase I of the study. With an expectation that 15% of the test sites will be positive, based on the selection of allergens with the highest incidence of reactions, and a target sensitivity of 95%, 90% power, and a minimum clinically relevant difference of 5 percentage points, a total of 130 positive test sites needs to be present in the study to achieve the design specifications. Given the assumption that most participants will only exhibit 1 to 2 reactions and the intraclass correlation of detections remains unknown, the design effect (or variance inflation effect) is not applied to account for potential clustering of reactions per participant. Therefore, with the assumption that each participant will have 1.5 positive reactions on average, we anticipate a requirement for 100 participants.

The sample sizes for Phase II and III have been administratively set based on feasibility of recruitment and testing.

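### The primary non-inferiority rule limits pooled accuracy to a 5-point loss, so an AI 10 points less sensitive than the human photo reader would usually pass at equal specificity; the sensitivity difference should be reported in the same conclusion

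*Combined protocol and SAP*

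**What the plan says.** - **Primary rule (section 7.2.2, Primary Hypothesis).** The claim is "The AI algorithm will provide non-inferior performance measured by binary classification accuracy relative to the human performance", and "a limit of inferiority of 5 percentage points will be used".
- **Model.** It is a GEE with identity link and robust variance: "The model will have a single predictor that indicates which reader (AI vs. human) is associated with the accuracy determination". Nothing in it separates sites that were positive in person from sites that were negative.
- **Accuracy target.** The same section adds that "we desire both the human and AI performance to provide greater than 95% accuracy". As worded this is a wish; the figure it refers to is not in the copy reviewed.
- **Sample size (section 7.1).** The inputs are "a target sensitivity of 95%, 90% power, and a minimum clinically relevant difference of 5 percentage points". The starting point is "With an expectation that 15% of the test sites will be positive". No test is named, and the 5 points are not called an AI-human margin.
- **Supporting measures (section 7.2.2).** Sensitivity, specificity, false positive rate and false negative rate are secondary endpoints. AUC is compared between readers by DeLong's test. The diagnostic measures are computed in two ways: "First, each test site will be assumed to be statistically independent in the rating", and then "an exploratory analysis will be conducted using generalized estimating equations to examine the impact" of within-participant correlation on precision.

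**The concern.** When few sites are positive, pooled accuracy is mostly agreement on negative sites. A limit of 5 points on accuracy is therefore not a limit of 5 points on sensitivity, the scale on which section 7.1 sizes the study. A 5-point sensitivity loss moves pooled accuracy by only 0.75 points at 15% positivity (0.15 × 5) and by 0.32 points at 6.4%.

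The trial could therefore report non-inferior performance for an AI that misses clearly more reactions than the human photo reader. The supporting measures would show this only in part. No AI-minus-human sensitivity difference with a participant-clustered confidence interval is specified, and no supporting result enters the stated conclusion.

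**Working it through.** **Inputs.** Limit 5 points (7.2.2). Positivity 15% (7.1) or 6.4%, which is 132/2,060 (1.3.2, Study #2). Phase 1 has 100 participants with 10 primary sites each (3.1, 5.2.1), so 1,000 sites. Assumed, because the documents give no human photo-read accuracy: human sensitivity 70, 80 or 95% and specificity 95, 96 or 98%. The rule is read in the usual way: the lower bound of the 95% CI for AI minus human must exceed −5 points.

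**The plan's own figures.** The plan does not convert its accuracy limit to sensitivity, so there is no figure of that kind to reproduce. Its 130 positive sites do not follow from the stated inputs by the usual formulas (a one-sample comparison of 95% with 90% at 90% power gives 221 one-sided or 264 two-sided). That is a separate matter and is not used here. The Study #2 figures do fit the identity below: 0.064 × 58.3 + 0.936 × 93.3 = 91.1%, against 91.0% reported; the gap is rounding.

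**Step 1: exact conversion.** With positivity p,

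accuracy difference = p × (sensitivity difference) + (1 − p) × (specificity difference).

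Set the accuracy loss to 5 points and solve for the sensitivity loss:

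| AI specificity relative to human | 15% positive | 6.4% positive |
|---|---|---|
| Equal | 0.05/0.15 = 33 points | 0.05/0.064 = 78 points |
| 1 point lower | (0.05 − 0.85 × 0.01)/0.15 = 28 | (0.05 − 0.936 × 0.01)/0.064 = 63 |
| 2 points lower | (0.05 − 0.85 × 0.02)/0.15 = 22 | (0.05 − 0.936 × 0.02)/0.064 = 49 |

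No reader accuracy is assumed in this step.

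**Step 2: one case by hand.** Take 15% positivity, human 95/95 (sensitivity/specificity), AI 85/95, independent errors.
- Mean difference: 0.15 × (−0.10) = −0.015.
- Per-site variance: 0.15 × (0.85 × 0.15 + 0.95 × 0.05) + 0.85 × (2 × 0.95 × 0.05) + 0.15 × 0.85 × 0.10² = 0.108.
- SE: √(0.108/1,000) = 0.0104.
- The estimate must exceed −0.05 + 1.96 × 0.0104 = −0.0296.
- z = (−0.0296 + 0.015)/0.0104 = −1.40, so the pass probability is about 92%.

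Fitting the actual identity-link GEE to 120 simulated trials gave 91%. The same hand calculation for a 75/95 AI gives 44% (GEE 49%).

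**Step 3: simulation over the nine assumed human readers.** At least 2,000 replicates per scenario, participant-clustered CI, positivity varying between participants (ICC 0.1), independent reader errors. Probability of being declared non-inferior:

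| AI sensitivity loss | AI specificity | 15% positive | 6.4% positive |
|---|---|---|---|
| 10 points | equal | 80–99% | 97–100% |
| 10 points | 1 point lower | 55–88% | 84–99% |
| 10 points | 2 points lower | 30–54% | 57–87% |
| 20 points | equal | 36–63% | 90–100% |
| 20 points | 1 point lower | 15–26% | 69–92% |
| 20 points | 2 points lower | 4–6% | 36–57% |

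**Step 4: error structure, 20-point loss at equal specificity.** Errors clustered within participant (latent correlation 0.2, then 0.4) lower the range to 26–51%, then 19–42%, at 15% positivity, and to 76–98%, then 61–93%, at 6.4%. Errors shared between the two readers (latent correlation 0.7) raise it to 50–74% and 98–100%.

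**The case against.** **The 33 and 78 points are not losses the rule lets through.** A reader might infer that they are. They are true losses exactly at the limit, and an AI truly there passes only about 2–3% of the time. This objection stands.

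**Equal specificity drives the largest figures.** The earlier algorithm had specificity of 93.3% in Study #2 and 95.6% in Study #1. With the Study #2 values (58.3/93.3) it would pass only about 0–32% of the time at 15% positivity, depending on the assumed human reader. This stands, and it is why the table shows lower AI specificity as well.

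**An AI that calls every site negative.** A reader might infer that it would pass. At the planned 15% it passes about 0% of the time. Only at 6.4% can it pass, about 87% against an 80/96 human but 14% against 95/98. The 6.4% may not carry over: section 1.3.2 does not give the grade cut-off behind it, while this endpoint counts doubtful reactions as positive.

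**Detection is already covered.** Sensitivity, specificity and a direct AUC comparison are prespecified, and the objective in section 2.1 is concordance, which accuracy does measure. So the documents do not support saying that detection is ignored or that accuracy is an invalid endpoint. But the clustered analysis of sensitivity is exploratory, no AI-minus-human sensitivity difference is specified, and no supporting measure has a role in the conclusion.

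**Section 7.1 names no test and no AI-human margin.** Correct. The mismatch is one of scale between sizing and decision, not a contradiction between two margins.

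**Conclusion.** The point holds in this form: the only stated success rule is a limit on pooled accuracy, and on its own it is a weak check on missed reactions. The conversion to 33 points (15% positivity) and 78 points (6.4%) at equal specificity is exact. The pass rates rest on the assumed human accuracy, 1,000 Phase 1 sites and independent errors. Under those assumptions and equal specificity, a 10-point sensitivity loss usually passes (80–99% and 97–100%), and a 20-point loss passes 36–63% of the time at 15% and 90–100% at 6.4%. If the AI is also 2 points less specific, the 20-point figures fall to 4–6% and 36–57%.

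A reader might go further and conclude that accuracy must be replaced as the primary measure. The documents do not require that: concordance is the stated objective, and the alternatives have real costs (see the fix). The analysis can run as written. What should change is what is reported beside the primary result and what is claimed from it.

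**What to change.** Keep accuracy primary. Suggested text for section 7.2.2:

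> The GEE will be fitted as planned and again with the in-person Day 5 result (positive/negative) and its interaction with reader, using the identity link and robust variance clustered on participant. AI-minus-human differences in sensitivity and in specificity will be reported with 95% CIs beside the accuracy difference. Meeting the 5-point limit on accuracy will be described as non-inferior overall agreement. No claim of non-inferior detection of reactions will be made from that result alone, and the sensitivity difference and its CI will be stated in the same conclusion.

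Also state whether accuracy above 95% is a success criterion or only a target.

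**Cost.** A small extra analysis and a narrower claim, with no new data and no loss of power for the accuracy test.

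**Option for the sponsor, not part of the required fix.** A balanced-accuracy or sensitivity margin could serve as a gate or a new primary. A 5-point limit on balanced accuracy still allows a 10-point sensitivity loss at equal specificity. Its power for a truly equal AI is about 95% at the design point (15% positive, 95% sensitivity), but about 44–57% at 15% with 70–80% sensitivity, and 23–75% at 6.4%. A 5-point limit on sensitivity alone has only 52–54% power at the design point.

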The overall incidence of allergic contact dermatitis in the sample was 6.4% (132/2,060) using the panel of allergens to be tested in the present study. The 206 images yielded 2060 test sites that were expertly evaluated during the in clinic (Day 5) evaluation. The only input to the neural network was the cropped image of the patch test site sites. The CNN model diagnosed the presence or absence of reaction with an AUROC of 0.861 (95% CI, 0.824 – 0.897). Using the previously selected cutoff of 4.88%, this generated an accuracy of 91.0% (95% CI, 89.7%-92.2%), a sensitivity of 58.3% (95% CI, 49.4%-66.8%), and a specificity of 93.3% (95% CI, 92.0%-94.3%).

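### The AI-versus-human AUC test ignores clustering within participants, and the clustered interval for specificity is planned only as exploratory

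*Combined protocol and SAP*

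**What the plan says.** All in Section 7.2.2 unless noted:

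- **Primary comparison.** Agreement with the in-person reading is modelled by GEE with a "robust variance estimator to account for the clustering within the database".
- **Supplementary AUC.** The AUC is "computed using the visual analog scale by test site determined by the human observer" and from the AI model's output. DeLong's "test will be used to compare the differences in performance between these two approaches". No clustered variance or participant-level bootstrap is named.
- **Sensitivity, specificity and similar measures.** These are calculated in two ways where feasible. "First, each test site will be assumed to be statistically independent in the rating". The reason given is: "For the neural network, this is how the algorithm functions". The plan accepts that human readings may be correlated, and for that reason "an exploratory analysis will be conducted using generalized estimating equations to examine the impact empirically the intercorrelations may have on the estimated precision". It does not say which of the two intervals will be reported as the result.
- **Section 7.1.** No design effect is applied, because most participants are expected to have 1 to 2 reactions and "the intraclass correlation of detections remains unknown".

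**The concern.** The same data, ten primary-patch sites per participant, are treated as clustered in the primary model and as independent in the AUC test that follows it. DeLong's method allows for two readers scoring the same sites. It does not allow for correlation between different sites of one person.

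The reason given for independence does not hold. A network that scores each site separately can still make correlated errors, because the sites share one person's skin type and skin reactivity. The phone cradle in Section 6.4 limits differences in lighting and distance, but not these.

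The argument in Section 7.1 does not help either. Few reactions per participant means few positive sites, which bears on sensitivity. Specificity rests on the negative sites, about 8.5 per participant.

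At stake are the confidence interval for specificity and false positive rate, both listed secondary endpoints, and the error rate of the AUC comparison between AI and human. Section 7.3.3 says all results will carry 95% intervals, so a reader will take these at face value.

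**Working it through.** **1. How the earlier study's intervals were obtained.** Section 1.3.2 gives 2,060 sites, of which 132 were positive, so 2,060 - 132 = 1,928 were negative. The printed percentages imply the counts below. Exact binomial (Clopper-Pearson) intervals with every site independent are:

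| Measure | Count | Exact interval, sites independent | Printed interval |
|---|---|---|---|
| Sensitivity | 77/132 = 58.3% | 49.4-66.8 | 49.4-66.8 |
| Specificity | 1,798/1,928 = 93.3% | 92.0-94.3 | 92.0-94.3 |
| Accuracy | 1,875/2,060 = 91.0% | 89.7-92.2 | 89.7-92.2 |

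All three agree with the printed intervals, which therefore make no allowance for participants.

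**2. Specificity, by formula.** Inputs: 10 sites per participant (Section 5.2.1), 15% positive and 100 participants (Section 7.1), hence 8.5 negative sites each and 850 in all. Specificity is set at 0.933 (Section 1.3.2). The ICCs are assumptions.

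- Design effect DE = 1 + (8.5 - 1) × ICC
- Shortfall of the naive standard error = 1 - 1/√DE
- Approximate coverage of a nominal 95% interval = 2Φ(1.96/√DE) - 1
- Half-width = 1.96 × √(0.933 × 0.067/850) × √DE = 1.68 points × √DE

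| ICC | DE | Naive SE too small by | Coverage | Half-width (points) |
|---|---|---|---|---|
| 0 | 1.00 | 0% | 95% | 1.68 |
| 0.02 | 1.15 | 7% | 93% | 1.80 |
| 0.05 | 1.38 | 15% | 91% | 1.97 |
| 0.10 | 1.75 | 24% | 86% | 2.22 |

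For sensitivity, with 1.5 positive sites per participant, DE at ICC 0.10 is 1 + 0.5 × 0.10 = 1.05.

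**3. Specificity, by simulation.** 10,000 trials per ICC, 100 participants, beta-binomial errors, positives Binomial(10, 0.15). The Monte Carlo standard error is √(0.95 × 0.05/10,000), about 0.2 points.

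| ICC | Independence exact: coverage | Cluster-robust, logit scale: coverage | Mean width of robust interval (independence 3.5 points) |
|---|---|---|---|
| 0.02 | 94.3% | 95.2% | 3.7 |
| 0.05 | 91.2% | 94.6% | 4.0 |
| 0.10 | 87.2% | 94.9% | 4.5 |

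For sensitivity at ICC 0.10 the independence interval covers about 95%.

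**4. AUC difference, by simulation.** Two readers with equal AUC 0.86, 100 participants × 10 sites, 15% positive, binormal scores, participant effects correlated 0 or 0.5 between readers, 6,000 trials per scenario. The Monte Carlo standard error is √(0.05 × 0.95/6,000), about 0.3 points. Type I error of paired DeLong at nominal 5%:

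| How reactions fall | Score ICC | DeLong |
|---|---|---|
| 1 or 2 in every participant | 0.1-0.4 | 3.5-4.7% |
| Independently across sites | 0.1-0.2 | 5.1-6.0% |
| Independently across sites | 0.4 | 7.5-7.8% |
| Reaction ICC 0.10 | 0.1 | 5.7-6.7% |
| Reaction ICC 0.10 | 0.2 | 6.7-7.9% |
| Reaction ICC 0.10 | 0.4 | 10.8-12.2% |

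The Obuchowski clustered variance gives 5.1-5.8% in all of these. A second simulation (2,000 trials per setting, AUC about 0.87, Monte Carlo standard error about 0.5 points) gave 5.5-6.3% for DeLong at score ICC 0.1 and 9.2-12.5% at 0.5, against 4.8-6.4% for the clustered version over all settings.

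The direction has a simple explanation. The AUC sets positive sites against negative sites, and a participant effect shifts both. If every participant has nearly the same share of positives, the shift largely cancels. If positives are concentrated in some participants, it does not.

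**The case against.** The strongest case against is about weight. The only confirmatory test already uses a robust variance. The AUC comparison is supplementary, with no margin or success rule, and specificity has no hypothesis attached. A GEE version of the diagnostic measures is already planned, with the stated aim of seeing what correlation does to interval width, so for specificity the dispute is mainly about which interval is the headline. If every participant has 1 or 2 reactions, close to what Section 7.1 expects, DeLong is slightly conservative. At the 6.4% positivity of the earlier study, with independent reactions, DeLong gave 4.7-6.4% and the clustered version 5.1-6.0%, which is no practical difference. Error above 10% needs a high score ICC together with clustered reactions, and the documents give neither. The intervals of a completed earlier study do not prove a fault in this plan.

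Most of this stands, and it limits the point to secondary results. It does not remove it. The planned GEE is exploratory, is motivated only by the human reading, has no rule for reporting, and does not extend to the AUC. The stated ground for independence remains wrong. A lower positivity does not help specificity: at 6.4% there are 9.36 negative sites per participant, and at ICC 0.10 DE = 1 + 8.36 × 0.10 = 1.84. The request for the logit scale is a matter of good practice and not a correction of an error.

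**Conclusion.** The point holds, for secondary and supplementary results only. If errors correlate within participants, the independence interval for specificity is too narrow: coverage of about 94%, 91% and 87% at assumed ICCs of 0.02, 0.05 and 0.10. DeLong's type I error depends on a correlation structure that the plan calls unknown. It lay between 3.5% and 12.2% over the scenarios examined, and a reader of the AUC result could not tell which value applies. At low ICC the effect on the AUC test is small.

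These sizes rest on assumed ICCs, binormal scores for the AUC, and the plan's 15% positivity. No claim is made about sensitivity, and the primary non-inferiority conclusion is unaffected.

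**What to change.** Amend Section 7.2.2 as follows:

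- Replace ordinary DeLong with a participant-clustered comparison of the two AUCs, using either the Obuchowski clustered-ROC variance or a bootstrap that resamples whole participants and keeps both readers' scores together.
- Name the GEE or cluster-robust interval, on the logit scale, as the reported interval for specificity and false positive rate, for both readers. Keep the independence calculation as a sensitivity analysis.
- Remove the statement that independence follows from how the network works.
- For consistency, use the same method for sensitivity and false negative rate, where little will change.

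The cost is SAP wording and a few lines of code, with no new data or participants. From the simulated mean widths, specificity intervals widen by 3.7 - 3.5 = 0.2 points at ICC 0.02 and 4.5 - 3.5 = 1.0 point at ICC 0.10.

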9.4. RECORDS RETENTION	29
10. STUDY MONITORING, AUDITING, AND INSPECTING	30
10.1. STUDY MONITORING PLAN	30
10.2. AUDITING AND INSPECTING	30
11. ETHICAL CONSIDERATIONS.....	30
11.1. CONFLICT OF INTEREST.....	30
11.2. SUBJECT STIPENDS OR PAYMENTS	31
12. REFERENCES.....	31

Study Summary

Title	Adaptive deployment of DermAI to evaluate human factors of testing
Running Title	User Adaptation
Protocol Number	DermAI-005
Phase	Other
Methodology	Prospective randomized controlled trial
Overall Study Duration	12 months
Subject Participation Duration	Participation will take approximately 1 week.
Single or Multi-Site	Single
Objectives	To develop the performance characteristics and human factor considerations to support fully remote patch testing.
Number of Subjects	Up to 10 pilot subjects followed by 150 Adaptive Patients
Diagnosis and Main Inclusion Criteria	
The condition being studied is allergic contact dermatitis
 
Inclusion Criteria:
 
 • Adults aged 18 or older • Able to provide consent
Study Product, Dose, Route, Regimen	
Device: AI algorithm to evaluate photographs of skin test patch regions
 
Drug: Allergens used in the testing protocol

Statistical Methodology	The analysis plan will focus on comparing the AI predictions of reactions with the interpretation of a human review of the photographs documented during the study visits. The reference criterion will be the expert, in person review as is currently performed with standard clinical operations.

Summary of Protocol Changes

Protocol Version	Summary of Key Changes
1.0	
• Original Protocol
1.1	
• Addition of 10 pilot subjects• Minor refinements to protocol details throughout
1.2	
• Addition of allergens and updates on Phase III activities.

1. Introduction

This document is a protocol for a human research study. This study will be carried out in accordance with the applicable United States government regulations and Mayo Clinic research policies and procedures.

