1.3. Preliminary Data

1.3.1. Study #1: IRB 19-012164

[figure not shown]
To-date, retrospective data collection under IRB 19-012164 has enrolled 310 subjects with 5,417 reaction photographs (approximately 54,170 individual reaction sites) which includes images taken both from the prior patch design as well as the new, fiducial patch design.

We have designed a deep learning classifier to predict the presence of allergic reaction from smartphone images of patch test reaction sites. The model was tested on a dataset of 260 patches (2,600 individual reactions) from several dozen individuals.

On the test dataset, the model displayed area under the ROC curve of 0.877. At a prediction cutoff of 10%, the model had an accuracy of 0.942, a sensitivity (true positive rate) of 0.540, and a specificity (true negative rate) of 0.956. The ROC curve is shown below, along with several examples of correct and incorrect predictions.

ROC curve for model performance at the reaction level

Examples of model prediction. For each of the four examples, the smartphone image of the reaction site is shown on the left, the true reaction label (based on the clinical report) is shown in the middle, and the model prediction is shown on the right. Positive and negative predictions are shown on a continuous color scale, where 1 (red) indicates the presence of reaction and 0 (blue) indicates the absence.

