5.6. Masking/Blinding of Study

The medical professional that reads the photographs of the test sites will be blinded to all clinical information including, but not limited to, the allergen's randomized locations, the in-person assessment of the reactions, and any AI predictions on the images. Effectively, the human read of the photograph will only have the photograph available to form all impressions about the reactions.

The reading of the human interpretation of the photographs will occur at least 1 month after the clinical visit to maintain blinding and washout in the event study staff provide a visual impression of the reaction sites via photographic review.

6. Study Procedures

6.1. Prior to Visit 1 and after study consent, the participant will have an opportunity to complete the Patient Journey. For Phases II and III of the study, this patient journey will be distributed to the patient prior to Visit 1 to allow for the data to be summarized. The summarization will include qualitative and quantitative approaches to quantify the self-reported employment profiles, ancestry, and known allergens to identify which allergens that may be more allergenic to the participant.

Visit 1 (Day 1)

Informed consent will be obtained as well as demographic information, medical history, and current medications questionnaire (see Schedule of Events).

A limited physical exam focused on the forearm will be conducted as well as assessment of participant's Fitzpatrick skin type.

A baseline photo will be taken using the smart phone application and the additional camera systems including the full spectrum documentation and photogrammetry acquisition.

A member of the study team will place the primary test patch on the volar aspect of participants' forearm. The patch contains allergens placed in dime-sized wells. The location of the allergens within the patch will be randomized between participants. The study team member will document the location of each allergen.

The smaller, 4 well patch, on the secondary arm will be placed similar manner to the primary test patch.

Tape or waterproof dressing may be used to secure the patch strips. Participant will be given instructions to avoid water contact with patch, and avoidance of sun exposure.

Participants will be allowed to take over the counter histamine blockers to alleviate pruritus.

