6.6. Reaction Grading Scale

Reactions will be graded as negative, irritant, or positive. Positive reactions will be rated as doubtful (1), weak (2), strong (3), or extreme (4) depending on their physical appearance. Doubtful reactions only have faint erythema, weak reactions are those with non-vesicular erythema, strong reactions are raised and have vesicular or non-vesicular erythema, extreme reactions are bullous or ulcerative in nature.

(Spiewak et al)

Symbol	Morphology	Assessment
-	No reaction	Negative reaction
?+	Faint erythema only	Doubtful reaction
+	Erythema, infiltration, possibly papules	Weak positive reaction
++	Erythema, infiltration, papules, vesicles	Strong positive reaction
+++	Intense erythema, infiltrate, coalescing vesicles	Extreme positive reaction
IR	Various morphologies, e.g. soap effect, bulla, necrosis	Irritant reaction

(Johansen et al)

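### The 5-point accuracy endpoint is analysed only as AI versus photo-reader kappa, so grading accuracy against the in-person reading is never estimated

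*Combined protocol and SAP*

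**What the plan says.** - **Endpoint.** The first secondary endpoint in section 7.2.2 is "The accuracy for the classification of the test site region using a 5-point scale", grades 0 to 4.
- **Reference.** The Study Summary states: "The reference criterion will be the expert, in person review as is currently performed with standard clinical operations". Sections 3.4 and 6.3 and the Schedule of Events fix this as the Day 5 in-person assessment.
- **Analysis.** Under Secondary Hypothesis 1, "unweighted and weighted Kappa will be used to estimate the degree to which the human and AI interpretations agree", and "The unweighted analysis will focus on the direct match on grade assigned to each of the test sites". The in-person grade is not named as a comparator, and the kappa weights are not stated.
- **Who the human is.** The primary hypothesis text in section 7.2.2 distinguishes the in-person clinical evaluation from the human review of app images. Section 5.6 blinds the photograph reader to the in-person result and says "the human read of the photograph will only have the photograph available to form all impressions about the reactions".
- **Other analyses.** The primary GEE scores each reader against the in-person review, but only after collapsing to grade 0 versus grades 1 to 4. The AUC, sensitivity and specificity are binary. The other planned kappa compares single with combined allergens.

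**The concern.** Accuracy needs a reference, and the plan has one. Kappa between the AI and the photograph reader measures whether two index readings agree with each other. It is symmetric, so it cannot show which of them is wrong, and accuracy against the in-person grade cannot be recovered from it.

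Shared mis-grading is plausible on the protocol's own account. Both readings come from photographs. Section 1.3.2 notes that a photograph reader cannot palpate, and section 1.2.1 hypothesises that 3D imaging carries tactile information that flat photographs lack. Yet the scale in section 6.6 separates grades partly by infiltration and papules. If both readings miss the same cue, AI-human kappa counts it as agreement. A high kappa alongside good binary accuracy could then be reported as good grading even though both readings understate the strength of reactions seen in person.

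**Working it through.** The documents give no precision, power or expected value for this endpoint, so there is no stated figure to reproduce. The check has two parts.

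**1. Which analysis can see which error**

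| Planned analysis | Comparator | Scale | Sees shared errors within grades 1-4? |
|---|---|---|---|
| Primary GEE | In-person | 0 vs 1-4 | No |
| Sensitivity, specificity and related rates | In-person | 0 vs 1-4 | No |
| AUC | Reaction status | Binary | No |
| Secondary Hypothesis 1 kappa | AI vs photograph reader | 0-4 | No |

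The only analysis on the full scale omits the reference. The analyses that use the reference collapse the scale.

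**2. How far apart the two quantities can be**

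Inputs:
- Positive sites: 15% (section 7.1), with 6.4% from the prior trial (section 1.3.2) as a check.
- Split of positive sites over grades 1 to 4: 30/40/25/5%. This is an assumption; the documents give none.
- The AI and photograph readings are identical, detect every positive and every negative site correctly, and place every grade 2 to 4 site one grade too low. This too is an assumption, a worst case and not an estimate.

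Per 1,000 sites, as (in-person grade, reader grade): (0,0) = 850; (1,1) = 45; (2,1) = 60; (3,2) = 37.5; (4,3) = 7.5.

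- AI versus human: the readings are identical, so kappa = 1.00 under any weights and any split. Binary accuracy, sensitivity and specificity are also 1.00.
- Exact-grade accuracy against in-person, all sites: (850 + 45)/1000 = 0.895.
- Exact-grade accuracy among in-person positive sites: 45/150 = 0.30.
- Chance agreement: 0.85×0.85 + 0.045×0.105 + 0.06×0.0375 + 0.0375×0.0075 + 0.0075×0 = 0.7298.
- Unweighted kappa against in-person: (0.895 − 0.7298)/(1 − 0.7298) = 0.611.
- Weighted kappa, as 1 minus observed over expected weighted disagreement: linear 1 − 0.02625/0.1137 = 0.769; quadratic 1 − 0.00656/0.0588 = 0.888.

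Varying the assumptions, with AI-human kappa and binary accuracy at 1.00 throughout:

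| Case | Exact, all sites | Exact, positive sites | Unweighted kappa vs in-person |
|---|---|---|---|
| Base, 15% positive | 0.895 | 0.30 | 0.611 |
| Half of grade 2-4 sites jointly under-graded | 0.948 | 0.65 | 0.806 |
| Split 20/40/30/10 | 0.880 | 0.20 | 0.558 |
| Split 70/20/8/2 | 0.955 | 0.70 | 0.829 |
| Base split, 6.4% positive | 0.955 | 0.30 | 0.635 |

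In the half-under-graded case the weighted kappas against in-person are 0.895 (linear) and 0.953 (quadratic).

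Symmetry: using the base table, if one reader is fully correct and the other is one step low on grades 2 to 4, AI-human kappa is 0.611 unweighted, 0.769 linear and 0.888 quadratic, whichever of the two is at fault.

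**The case against.** The strongest reply is that the omission is one of wording. Earlier in section 7.2.2 agreement is framed as in-person evaluation against both the human review and the AI, and accuracy is defined as matching the in-person review. Sections 2.1 and 2.2 state the AI and photograph-review objectives as concordance with in-person reading. A reader could carry that comparator into Secondary Hypothesis 1, or take the open-ended list of standard diagnostic measures later in section 7.2.2 to include graded accuracy. That intention is possible. But the sentence as written pairs AI with human, section 7.3.2 again speaks of concordance between those two, and no grade-level method against the reference is named anywhere. On either reading the same clause has to be written.

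The second reply is that the illustration is constructed, and that the low figure is for positive sites, which is not the listed endpoint. This is fair. The documents support neither identical readers nor perfect detection: AI sensitivity in sections 1.3.1 and 1.3.2 was 0.540 and 58.3%. Over all sites exact-grade accuracy stays between 0.88 and 0.955 in the cases above, because most sites are grade 0. The example shows that the planned statistic can hide mis-grading; it does not show that it will.

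The third reply is limited consequence, and it stands: this is a secondary endpoint with no success threshold and no role in the sample size, and no objective mentions reaction strength.

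**Conclusion.** The concern holds. Followed as written, the plan gives a statistic that does not estimate its own listed 5-point accuracy endpoint, and no planned analysis detects errors within grades 1 to 4 that the two photograph-based readings share. This rests on the text alone. The size of the possible discrepancy rests on the assumed grade split and on fully shared errors: with AI-human kappa at 1.00, exact-grade accuracy among positive sites ranges from 0.20 to 0.70, and unweighted kappa against the in-person grade from 0.56 to 0.83. Errors that cross the grade 0/1 boundary remain visible, and the primary non-inferiority conclusion is untouched. The point should be corrected, but its reach is confined to claims about grading.

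**What to change.** Rewrite Secondary Hypothesis 1 so that the in-person Day 5 grade is the comparator:

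- Report exact-grade accuracy, and unweighted and weighted kappa with the weights stated, for AI versus in-person and for photograph reader versus in-person.
- Report the difference between the two readers with a participant-clustered 95% CI, by GEE or by bootstrap over participants.
- Also report exact-grade accuracy among reference-positive sites, since grade 0 sites dominate the overall figure.
- Keep AI-versus-human kappa as descriptive.

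Two rules must be prespecified, and the kappa now planned needs them as well. The first maps the AI output to grades 0 to 4. Section 1.3.2 reports only that "The CNN model diagnosed the presence or absence of reaction with an AUROC of 0.861", and section 1.3.1 that "Positive and negative predictions are shown on a continuous color scale"; neither describes a graded output. The second states how irritant readings enter the analysis, because section 6.6 says "Reactions will be graded as negative, irritant, or positive" and gives irritant no place on the 0 to 4 scale.

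The cost is SAP wording, those two rules and a few more tabulations. In-person grading is already planned in sections 6.2, 6.3 and 6.6, so no new data are needed.
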